	 Assessment of clinical response: Development of CAV Graft loss Recipient mortality Acute and chronic rejection Opportunistic infections Cardiac function Renal function Description of non-DLT adverse events and those occurring beyond week 4 post Treg infusion Immunosuppressive doses 		
	Number of study visits completed per narticipant		
	Responses to items in questionnaires or surveys		
	exploring the study and treatment experience of		
Sampla Siza	9 participants that could be expanded to 12 in case		
Sample Size	of DLTs		
Summary of eligibility criteria	Inclusion criteria:		
	1. Male or female children aged between 0.5 and		
	10 years.		
	3 Children receiving a heart transplant		
	4. Single transplanted organ.		
	5. Willing and able to comply with the study visit		
	schedule.		
	Exclusion Criteria:		
	1. Active viral infection.		
	2. Age under 0.5 year or over 16 years.		
	3. Multi-organ transplant.		
	4. Highly-sensitised patients at high risk of		
	5 Allergy to any component/excinients used for		
	the manufacture of the Tree product.		
	6. Previous recipient of any organ transplant.		
	7. History of previous sternotomy surgical		
	procedure for congenital heart defect during		
	which has had previous partial or full		
	tnymectomy.		
	with absent thymus		
	9. Participation in another interventional Clinical		
	Trial of an Investigational Medicinal Product.		
	10. Pregnant and lactating patients.		
	11. Female patients of childbearing potential who		
	are not willing to use a highly effective method		

	of contraception.
	12. Male patients who are not willing to use an
	effective method of contraception.
	13. Patient is considered by the Chief Investigator
	to be an unsuitable candidate for the study.
Investigational medicinal product and	Autologous thymus derived Tregs (TR006) infused at
dosage	one of two doses in a 3+3 design:
	1. Low dose: 1 - 3 x 10 ⁶ Tregs/Kg
	or
	2. High (and highest) dose: 5 - 10 x 10 ⁶ Tregs/Kg
Active comparator product(s)	N/A
Route(s) of administration	Intravenous infusion.
Maximum duration of treatment of a	Each participant receives one infusion of autologous
subject	thymus derived Tregs at 3 - 6 months post
	transplantation and will be followed up for 24
	months post infusion.
Procedures for safety monitoring	DLT will be determined from data collected during
during trial	the 4-week period post Treg infusion
Definition of end of trial	Database Lock

Table of Contents

A	obreviations	5			
St	Study Synopsis7				

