1.1 Background

Heart transplantation is a lifesaving procedure for some children. However, the long-term success of a heart transplant is often limited by inflammatory processes leading to progressive narrowing of blood vessels that supply oxygen to the heart, known as Coronary Allograft Vasculopathy (CAV).

CAV is a leading cause of death beyond 3 years after heart transplant and remains an important limitation to long term survival and graft longevity [1]. Once established, CAV is refractory to conventional medical or surgical approaches, and constitutes the most important predictor for all-cause mortality in this patient population. Data from 2017 derived from angiography reports found that 67% of patients (of all ages) were free from CAV 10 years after their transplant [2]. However, early onset of disease or the true burden of disease may be well underestimated as coronary angiography is not the most sensitive modality of diagnosis. Once a diagnosis of CAV has been confimed, graft survival is also significantly reduced across all age groups, with infants being the worst affected (with a median survival of 2 years after diagnosis) [2].

CAV can occur despite the use of immunosuppressive drugs that are also linked to morbidity and mortality themselves, with side effects including increased risk of infection, reactivation of viruses and Post-Transplant Lymphoproliferative Disorder (PTLD).

No effective treatments are available for established CAV. Revascularization has not shown to improve outcome and re-transplantation is limited by donor availability. Re-transplantation is rarely possible due to donor shortages and the presence of alloantibodies induced by the previous transplant.

Recent data from a multicentre study, involving GOSH, showed that impaired graft function associated with CAV was a poor prognostic sign [3]. Interestingly, the incidence of CAV in children has not declined over time. Therefore, the prevention of CAV, the main cause of graft damage, is still an unmet goal. The urgency is reflected by the clear directive from the Family Steering Group at Great Ormond Street Hospital.

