- 2. The TR001 phase I/II study based at Oxford and King's College London (NCT02129881) comprised 15 patients who were enrolled into the trial; 2 patients were withdrawn due to failure to expand sufficient Tregs (n=2) and one due to bacterial contamination of the Treg product. Out of 12 remaining patients, there were no Serious Adverse Reactions (SARs) or episodes of graft rejection, and a lower incidence of opportunistic infections compared to the reference group. Participants received cell therapy alongside standard of care immunosuppression. Infused cell doses are shown in Table 1. In a new currently ongoing trial, TR001 is being administered to living-donor kidney transplant recipients as part of a single centre phase II trial The TWO Study. The overall aim of this study is to evaluate the efficacy of Tregs in renal transplantation [9].

Results of the King's College London and Oxford study were pooled and published as with the ONE study, with a detailed paper of the Treg trial to follow [10]. Analysis of the adverse event data showed no safety issues when compared to the reference group trial. Infection rates were lower in the trials of cell-based medicinal products but the rejection rate was found to be similar across all trials.

Another phase I study (NCT02088931) from University of California treated 3 renal transplant recipients with an absolute Treg cell dose each of 319, 321 and 364x10⁶ (equivalent to 4.5x10⁶/kg, 4.6x10⁶/kg and 5.2x10⁶/kg assuming a body weight of 70kg). There were no opportunistic infections or SAEs, no CMV or polyoma neuropathy, no rejection, or cases of donor specific antibodies at one-month post infusion [26].

Autoimmune disorders

Clinical trials using autologous expanded Tregs have been conducted in specific autoimmune disorders, namely type I diabetes, and systemic lupus erythematosus, summarised in **Table 1** below).

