3.2 Objectives and endpoints

Objectives	Outcome Measures/Endpoints
Primary Objective: To determine safety and optimal tolerated dose of TR006 to prevent CAV in paediatric heart	Primary Endpoint: Occurrence and nature of Dose-Limiting Toxicities (DLTs) occurring within 4 weeks post-
transplant patients in a phase I study.	infusion of the expanded autologous thymus derived Treg product (ATIMP).
Secondary Objectives:	Secondary Endpoints:
1. To assess the feasibility of generating TR006 in the Good Manufacturing Practice facility.	Amount of TR006 manufactured per patient.
2. To investigate the clinical and immunological	Assessment of Immunological response:
responses to TR006 in paediatric heart	• Frequency of circulating leukocyte subsets.
transplant patients.	• Quantity of alloantigen-specific conventional T cells, Tregs and CD8+.
	 Presence of anti-HLA to evaluate tissue infiltrating cells.
	Assessment of clinical response:
	• Diagnosis of CAV as measured by coronary angiography within 24 months post-infusion of TR006.
	 Graft loss as measured by inclusion of patient on the re-transplant waiting list through rejection (acute or chronic) within
	24 months post-infusion of TR006.
	• Recipient mortality within 24 months post- infusion of TR006.
	 Acute graft rejection as measured by endomyocardial biopsy (EMB) within 24 months post-infusion of TR006.
	• Antibody-mediated rejection as measured by development of donor specific antibodies within 24 months post-infusion of TR006.

r	
	 Infection related rehospitalisation events within 24 months post-infusion of TR006.
	 (Cardiac function) Left ventricular ejection fraction as measured by echocardiography monthly for 12 months and at 24 months post-infusion of TR006.
	 (Renal function) Mean calculated GFR at 24months post-infusion of TR006.
	• Description of non-DLT adverse events and those occurring beyond week 4 and up to 24 months post-infusion of TR006.
	 Immunosuppressive doses at 12 and 24 months post-infusion of TR006.
3. To assess the feasibility of retaining participants for the duration of the study and completion of study visits and assessments	Number of study visits completed per participant.
	 Responses to items in questionnaires or surveys exploring the study and treatment experience of the participants and their parents/guardians.

4 Assessment and Management of Risk

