6.1 Inclusion Criteria

- 1. Male or female children aged between 0.5 and 16 (inclusive) years of age at date of consent/assent and date of transplant.
- 2. Written informed consent obtained from a parent/legal guardian.
- 3. Registered on the heart transplant list at date of consent and received a heart transplant on enrolment.
- 4. Receiving a single transplanted organ.
- 5. Willing and able to comply with the study visit schedule.

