7.5 Subsequent Visits

Safety Follow-up: Days 2 - 13 post TR006 infusion. (+/- 2 days)

- Concomitant medication collection. (All visits)
- Adverse Events collection. (All visits)
- Remote doctor review. (All visits)

Safety Follow-up: Days 14 post TR006 infusion. (+/- 2 days)

- Concomitant medication collection.
- Adverse Events collection.
- Doctor review (including physical examination).
- Vital signs.
- Height and weight.
- ECG (12-Lead).
- Echocardiography.
- Clinical blood test (Full blood count, liver profile, renal profile, LDH, EBV and CMV viral load).
- Translational research blood samples.

Safety Follow-up: Days 28 post TR006 infusion. (+/- 2 days)

- Concomitant medication collection.
- Adverse Events collection.
- Doctor review (including physical examination).
- Vital signs.
- Height and weight.
- ECG (12-Lead).
- Echocardiography.
- Clinical blood test (Full blood count, liver profile, renal profile, LDH, EBV and CMV viral load).
- Translational research blood samples.

Safety Follow-up: Month 2 post TR006 infusion. (+/- 1 week)

- Concomitant medication collection.
- Adverse Events collection.
- Doctor review (including physical examination).
- Vital signs.
- Height and weight.
- ECG (12-Lead).
- Echocardiography.
- Clinical blood tests (Full blood count, liver profile, renal profile, LDH, EBV and CMV viral load.

Safety Follow-up: Month 3 post TR006 infusion. (+/-1 week)

- Concomitant medication collection.
- Adverse Events collection.
- Doctor review (including physical examination).

- Vital signs.
- Height and weight.
- ECG (12-Lead).
- Echocardiography.
- Clinical blood tests (Full blood count, liver profile, renal profile, LDH, EBV, CMV viral load, full blood borne infectious diseases screen and HLA antibody testing (includes panel reactive antibodies and donor specific antibodies)).
- Urine pregnancy test (if applicable).
- Translational research blood samples.
- Clinical cardiac biopsy.

Safety Follow-up: Month 6 post TR006 infusion. (+/- 2 weeks)

- Concomitant medication collection.
- Adverse Events collection.
- Doctor review (including physical examination).
- Vital signs.
- Height and weight.
- ECG (12-Lead).
- Echocardiography.
- Clinical blood tests (Full blood count, liver profile, renal profile, LDH, EBV and CMV viral load).
- Translational research blood samples.

Safety Follow-up: Month 9 post TR006 infusion. (+/- 2 weeks)

- Concomitant medication collection.
- Adverse Events collection.

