7.9 Post treatment follow-up

Participants will be followed-up for 24 months post-treatment.

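### The synopsis names opportunistic infection as an endpoint, but section 3.2 measures only infection-related rehospitalisation, a different event, and the adverse-event record covers the gap only to Month 12

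*Protocol*

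**What the plan says.** The Study Synopsis lists the items for assessing clinical response. In the extracted text they run together as "Acute and chronic rejection Opportunistic infections Cardiac function Renal function". Opportunistic infection is therefore a named secondary endpoint.

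Section 3.2 gives each objective its outcome measure. Opportunistic infection is not there. The only infection item under clinical response is "Infection related rehospitalisation events within 24 months post-infusion of TR006". It is not limited to any organism or class of infection.

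Section 3.2 also has a general endpoint describing adverse events that are not DLTs, or that occur after week 4, up to 24 months after infusion. Section 7.9 sets the same horizon: "Participants will be followed-up for 24 months post-treatment". Sections 9.3 and 9.4, however, record adverse events, including serious ones, from screening to the Month 12 visit, and only SUSARs from Month 12 to Month 24. Section 7.5 and Table 5 nevertheless schedule adverse-event collection at Month 24.

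Viral loads are part of the routine blood tests at the in-person follow-up visits. The Day 14 entry in section 7.5 reads "Clinical blood test (Full blood count, liver profile, renal profile, LDH, EBV and CMV viral load". The key to the schedule of events makes the viral loads conditional on need.

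Section 10.1 summarises most secondary endpoints as rates with 95% confidence intervals.

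**The concern.** These are not a short and a long form of one endpoint. One is defined by the kind of infection, the other by whether the child was admitted. A reader of the synopsis expects a count of opportunistic infections, and a report that follows section 3.2 would not contain one.

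The protocol itself treats such infections as important. Section 1.1 says that immunosuppressive drugs carry "side effects including increased risk of infection, reactivation of viruses and Post-Transplant Lymphoproliferative Disorder (PTLD". Section 4.3 leaves standard tacrolimus and mycophenolate unchanged, so the cells are added to full immunosuppression, and excess immunosuppression is a natural safety question. Section 1.4 supports the product partly with viral and opportunistic infection results from earlier trials, for example "a lower incidence of opportunistic infections compared to the reference group" in one renal study.

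The study enrols "Male or female children aged between 0.5 and 16 (inclusive) years of age". In the youngest, an admission for a common infection is a likely event. An admission count can therefore be raised by events that say little about opportunistic infection, and can stay at zero in a child with viral reactivation managed as an outpatient.

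The statistical analysis plan cannot settle this alone. It can supply a definition, but it should not have to choose between two endpoints that the protocol names.

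**Working it through.** The protocol gives no figure to reproduce. The check sets its sections side by side, with one count of visits.

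**1. Do the two endpoints coincide?**

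| Event after infusion | Synopsis item | Section 3.2 item |
|---|---|---|
| Opportunistic infection, managed without admission | counts | does not count |
| Opportunistic infection, admitted | counts | counts |
| Ordinary childhood infection, admitted | does not count | counts |
| Ordinary childhood infection, not admitted | does not count | does not count |

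The first and third rows disagree in opposite directions, so neither endpoint contains the other. Whether a viral-load rise without symptoms belongs in the first row depends on a definition that the protocol does not give. Under section 3.2 it does not count unless the child is admitted.

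**2. Where else could a missed case appear?**

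- *Primary endpoint.* Section 5.1 makes a related infection of CTCAE grade 3 or higher a DLT, but only in the first 4 weeks.
- *General adverse-event endpoint.* Section 9.1.1 includes abnormal laboratory findings in the definition of an adverse event. A viral-load rise reported as such would reach this endpoint.
- *After Month 12.* Only SUSARs are reported. An infection that is not serious, or not judged related, has no stated recording route. Section 9.1.3 makes an admission a serious event, so an unrelated infection admission after Month 12 also falls outside the stated rule, although the section 3.2 item runs to 24 months. A separate eCRF page could capture it, but the protocol does not mention one.

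**3. How much of the window is covered?**

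The endpoint window is 24 months and adverse-event recording runs to Month 12. Uncovered: 24 − 12 = 12 months, or 12/24 = 50%.

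**4. What viral-load data are already scheduled?**

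Section 7.5 lists EBV and CMV viral load at Days 14 and 28 and Months 2, 3, 6, 9, 12 and 24, which is 8 visits.

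- 9 children: 8 × 9 = 72 visit results, of which 7 × 9 = 63 fall by Month 12 and 1 × 9 = 9 at Month 24.
- 12 children, if the study is expanded: 8 × 12 = 96.

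These are ceilings, because the schedule key makes the test conditional. Day 0 (before dosing and 6 hours after) and Day 1 are left out, since they say little about reactivation after the infusion. No endpoint in section 3.2 names any of these results.

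**The case against.** The strongest reply is that the trial would still report these infections. A reader might infer from the mismatch that outpatient viral reactivation goes unreported altogether. The documents do not support that up to Month 12: an abnormal laboratory result can be an adverse event, adverse events are described under a section 3.2 endpoint, and a severe related infection in the first 4 weeks is a DLT. What remains is that such cases are not counted as the infection endpoint, and that the adverse-event route closes at Month 12 except for SUSARs.

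A reader might also infer that an admission count cannot be compared with any earlier Treg trial. That goes too far. The paediatric diabetes study in section 1.4 is summarised by serious infections and by ordinary mild ones, and admission is close to the first of these. The comparison fails only for the trials summarised by viral or opportunistic infection. The protocol does not give those trials' definitions, so a new endpoint would not be comparable automatically either.

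It is tempting to add that a child still in hospital after transplant cannot be rehospitalised. This is marginal: dosing is 3 to 6 months after transplant, with an overnight stay and discharge.

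Finally, this is one descriptive secondary endpoint in 9 to 12 children, and the contradiction could be removed by changing the synopsis instead. Both statements are right. The second would make the document consistent but would drop the infection outcome that the protocol's own background emphasises.

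**Conclusion.** The contradiction holds: the synopsis and section 3.2 name different infection endpoints, and following section 3.2 would not deliver the one in the synopsis. The general adverse-event description is a partial safety net that covers 12 of the 24 months. For the remaining 12, sections 9.3 and 9.4 conflict with the 24-month window in section 3.2 and with the adverse-event review scheduled at Month 24.

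This rests on reading section 3.2 literally and on no separate infection form existing outside the protocol. The visit count is a ceiling and shows only that usable data are already planned. It does not mean that 72 informative results would be lost.

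The consequence is limited to secondary safety reporting. No DLT decision, dose decision, stopping rule or sample size depends on it. It should be corrected, but it does not threaten the design.

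**What to change.** 1. In section 3.2, list opportunistic infection as its own endpoint within 24 months, matching the synopsis and counted whether or not the child is admitted.
2. Define it in advance, in the protocol or by reference to the statistical analysis plan, using recorded infection events and the scheduled EBV and CMV viral loads. The investigators should set the criteria; the protocol contains no viral-load threshold to borrow.
3. Report viral-load rises separately from clinical infection. A newly detectable viral load is not in itself an opportunistic infection, and in young children it may be a first community-acquired exposure.
4. Keep infection-related hospitalisation as a separate line.
5. Amend sections 9.3 and 9.4 so that infection events are recorded to Month 24, and reconcile them with section 7.5 and Table 5. State whether the viral loads are taken at every listed visit or only when needed.

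No new test or visit is required. The cost is a little more event recording in Months 12 to 24 and possibly a higher reported infection count. One limit remains: no visit is scheduled between Month 12 and Month 24, so non-admitted infections in that year would rest on recall and medical records at the final visit.

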4.1 IMP Risks

The Investigator's Brochure (IB) contains the reference safety information for TR006. For the Non-Investigational Medicinal Products (NIMPs) (details in **8.11** Non-Investigational Medicinal Products (NIMPs) below), investigators should refer to the relevant summary of product characteristics (SmPC) for the possible adverse drug reactions that may be experienced by trial patients. The risk-benefit profile of this clinical trial essentially balances the expected clinical benefits of minimising maintenance immunosuppression against the potential clinical complications that may result from the infusion of the Treg product.

This clinical trial has been designed to reduce the level of foreseeable risk, wherever this is possible. The clinical assessments specified by this protocol are largely those suggested by normal clinical guidelines and will not present risks that extend beyond the normal hazards associated with the routine clinical follow-up of paediatric heart transplant recipients. Tests required prior to patient enrolment (to assess eligibility) are also largely within the boundaries of standard clinical practice.

4.2 Risks associated with the administration of the Treg cell product

The potential risks associated with Treg therapy can be categorised as immunological, physiological, infectious, or due to adverse interactions with other treatments. While the single ascending dose design combined with safety reviews after the first and last dose of each dosing cohort, should minimise these risks, it is nonetheless necessary to consider the potential risks in turn.

4.2.1 Immunological Complications

The possible immunological complications of Treg therapy are broadly similar to those associated with blood transfusions, but with the important difference that the cells to be administered are from the patient themselves and are thus autologous. However, it is not possible to rule out unintended outcomes such as non-specific cytokine release triggered by cell infusion.

Hypersensitivity Reactions

Type I hypersensitivity reactions

Antigenic challenge can drive the production of IgE which binds to the FccRI receptor on mast cells and basophils leading to degranulation and the release of vasoactive and spasmogenic mediators, and proinflammatory cytokines. The clinical manifestation of such reactions varies in degree from relatively mild urticaria and pruritis to anaphylactic shock. Generalised pruritis and urticarial reactions can occur during blood transfusions, though typical incidence is of the order of 1 - 3%. These complications generally respond to parenteral antihistamines. Bronchospasm, laryngeal oedema, bradycardia and profound hypotension are uncommon occurrences during blood transfusions, but are potentially life-threatening and demand emergency treatment.

The possibility of hypersensitivity reactions against cellular antigens or excipients in Treg preparations cannot be discounted entirely but the fact that the infused cells are autologous indicates that the risk is low. The cell product will be infused in Cryostor CS10 medium (10% DMSO) and for this reason known allergies to components of the infusion are listed as exclusion criteria.

Patients will be admitted as an inpatient for administration of TR006, so that they can be closely monitored for signs of anaphylaxis or to receive emergency treatment should it be necessary. To prevent minor pruritic or urticarial reactions, patients will be treated prophylactically with an antihistamine 30 minutes before the planned infusion.

Type II hypersensitivity reactions

Antibodies against Treg cell-surface antigens, which may be intrinsic to the cell membrane or merely antigens adsorbed to the cell surface, can be responsible for a variety of adverse transfusion-associated reactions, including haemolytic transfusion reactions, post-transfusion purpura and some febrile reactions. A febrile transfusion reaction is defined as a 1°C rise in temperature during or within 3 hours of transfusion which cannot be attributed to sepsis or a haemolytic reaction. Febrile transfusion reactions may be accompanied by chills, rigors or pain. The incidence of febrile reactions to leuko-depleted blood products is approximately 1 in 330 for erythrocyte transfusions and 1 in 20 for platelet transfusions. Treatment consists of stopping the transfusion and providing supportive care, including antipyretic treatment.

Patients receiving TR006 will be prophylactically treated with paracetamol and an oral antihistamine prior to cell infusion. In the event of a 1°C rise in temperature, the rate of cell infusion will initially be slowed; if the febrile reaction persists, the infusion will be stopped.

Type III hypersensitivity reactions

Although once a common sequela to the administration of foreign serum for passive immunisation, serum sickness is now encountered infrequently. The pathogenesis of this systemic immune complex disease involves the deposit of antibody-antigen complexes in the tissues resulting in inflammation. Depending on their distribution, immune complexes cause vasculitis, glomerulonephritis or arthritis. Despite systemic immune complex disease not being a recognised complication of conventional transfusions, the possibility of Type III hypersensitivity responses after Treg administration cannot be completely excluded. However, since TR006 is autologous to the patient, such complications are

considered unlikely. Clinicians responsible for patient care will be informed of the theoretical possibility of immune complex disease so that it might be considered as a possible cause if post-infusion complications are seen.

Non-specific adverse reactions

Release of pyrogenic cytokines upon systemic infusion of cell products can cause febrile reactions. In tissue culture, human Tregs produce detectable amounts of IL-6 and TNF- α , so could potentially cause fever after administration. Mild febrile responses do not constitute a major clinical concern and could be largely prevented by treatment of recipients with an antipyretic and anti-histamine prior to Treg infusion.

Unintended immune sensitisation

The Treg cell product in this trial is autologous and will be subject to stringent quality control testing and QP release (refer to IMPD). Therefore, immune sensitisation is unlikely. However, in the event of a cytokine storm then supportive measures may be supplemented by the administration of then anti-thymocyte globulin (ATG). This is a highly effective treatment for the deletion of all T cells and is in routine use in the treatment of severe rejection in heart transplant recipients. Basiliximab will be avoided as repeat basiliximab increases the risk of allergic reaction. Other treatments may be administered on a case by case basis in line with Trust SOPs.

Transfusion-Related Acute Lung Injury (TRALI)

A well-recognised and clinically important complication of blood transfusion is non-cardiogenic pulmonary oedema, referred to as transfusion-related acute lung injury or TRALI, which occurs in roughly 1 in 5000 cases. The pathophysiology of TRALI is not completely understood, but neutrophil and platelet activation, and consequent damage to the pulmonary vascular endothelium are crucial components of the disease.

There is no evidence to suggest that Tregs should activate neutrophils in the lung and this complication has not been reported in published clinical trials of expanded naturally occurring Tregs. However, given the seriousness of the condition, all precautions will be taken to avoid it. A two-hit hypothesis has been advanced to explain the susceptibility of patients to TRALI, where neutrophil activation prior to transfusion predisposes to a detrimental neutrophil-mediated response when anti-leucocyte antibodies or other neutrophil-stimulating factors are subsequently administered.

